4.2.2 Efficacy

No clinical efficacy data will be obtained in the study.

4.2.3 Safety

There are no secondary objectives for safety.

4.3 Observational Endpoints and Assessment Methods

4.3.1 Immunogenicity

There are no observational objectives for immunogenicity in this study.

4.3.2 Safety

4.3.2.1 Safety Definitions

The following definitions are taken from the International Conference on Harmonization ICH E2A Guideline for Clinical Safety Data Management: Definitions and Standards for Expedited Reporting.

Adverse Event (AE):

An AE is any untoward medical occurrence in a patient or in a clinical investigation subject administered a medicinal product and which does not necessarily have a causal relationship with this treatment. An AE can therefore be any unfavorable and unintended sign (including an abnormal laboratory finding, for example), symptom or disease temporally associated with the use of a medicinal product, whether or not considered related to the medicinal product.

Therefore, an AE may be:

- A new illness
- The worsening of a pre-existing condition
- An effect of the vaccination, including the comparator
- A combination of the above
- All AEs include serious and non-serious AEs.
- Surgical procedures are not AEs; they are the actions taken to treat a medical condition. It is the condition leading to the action taken that is the AE (if it occurs during the study period).

Pre-existing medical conditions are not to be reported as AEs. However, if a pre-existing medical condition worsens following study interventions in frequency or intensity, or if according to the Investigator there is a change in its clinical significance, this change should be reported as an AE (exacerbation). This applies equally to recurring episodes of pre-existing conditions (e.g., asthma) if the frequency or intensity increases post-vaccination.

Serious Adverse Event (SAE):

Serious and *severe* are not synonymous. The term *severe* is often used to describe the intensity of a specific event as corresponding to Grade 3. This is not the same as *serious* which is based on subject / event outcome or action criteria usually associated with events that pose a threat to a subject's life or functioning. Seriousness, not severity, serves as a guide for defining regulatory reporting obligations.

An SAE is any untoward medical occurrence that at any dose

- Results in death
- Is life-threatening
- Requires inpatient hospitalization or prolongation of existing hospitalization
- Results in persistent or significant disability / incapacity
- Is a congenital anomaly / birth defect
- Is an important medical event (IME)

Medical and scientific judgment should be exercised in deciding whether expedited reporting is appropriate in other situations, such as IMEs that may not be immediately life-threatening or result in death or hospitalization but may jeopardize the health of the subject or may require intervention to prevent one of the other outcomes listed in the definition above. These IMEs should also usually be considered serious. Examples of such events include allergic bronchospasm requiring intensive treatment in an emergency room or at home, blood dyscrasias or convulsions that do not result in inpatient hospitalization, or the development of drug dependency or drug abuse, new-onset diabetes, or autoimmune disease.

Adverse Reaction:

All noxious and unintended responses to a medicinal product related to any dose should be considered ARs.

(The phrase “responses to a medicinal product” means that a causal relationship between a medicinal product and an AE is at least a reasonable possibility).

The following additional definitions are used by Sanofi Pasteur:

Immediate Event/Reaction:

Immediate events are recorded to capture medically relevant unsolicited systemic AEs (including those related to the product administered) that occur within the first 30 minutes after vaccination.

Solicited Reaction:

- 1) A solicited reaction is an “expected” AR (sign or symptom) observed and reported under the conditions (nature and onset) prelisted in the protocol and CRB.
- 2) By definition, solicited reactions are to be considered as being related to the product administered.

For injectable vaccines, solicited reactions can either be solicited injection site reactions or solicited systemic reactions.

The assessment of these reactions by the investigator is mandatory.

Unsolicited AE / AR:

An unsolicited AE is an observed AE that does not fulfill the conditions prelisted in the CRB in terms of diagnosis and/or onset window post-vaccination. For example, if vomiting between D0 and D7 is a solicited reaction (ie, prelisted in the protocol and CRB), then a vomiting starting on D7 is a solicited reaction, whereas vomiting starting on D8 post-vaccination is an unsolicited AE. Unsolicited AEs includes both serious (SAEs) and non-serious unsolicited AEs.

Injection Site Reaction:

An injection site reaction is an AR at and around the injection site. Injection site reactions are commonly inflammatory reactions. They are considered to be related to the product administered.

Systemic AE:

Systemic AEs are all AEs that are not injection or administration site reactions. They therefore include systemic manifestations such as vomiting, fever, as well as localized or topical

manifestations that are not associated with the vaccination or administration site (e.g., erythema that is localized but that is not occurring at the injection site).

Adverse Event of Special Interest (AESI):

An AESI is an event for which ongoing monitoring and rapid communication by the Investigator to the Sponsor must be done.

Such an event might warrant further investigation in order to characterize and understand it. Depending on the nature of the event, rapid communication by the study Sponsor to other parties (e.g., regulators) might also be warranted.

4.3.2.2 Safety Endpoints

The observational endpoints for the evaluation of safety are:

- Occurrence, nature (Medical Dictionary for Regulatory Activities [MedDRA] preferred term), duration, intensity, relationship to vaccination, and whether the event led to early termination from the study, of any unsolicited systemic AEs reported in the 30 minutes after each vaccination
- Occurrence, time of onset, number of days of occurrence, intensity, action taken, and whether the reaction led to early termination from the study, of solicited (prelisted in the subject's diary card and CRF) injection site reactions occurring up to D07 after each vaccination
- Occurrence, time of onset, number of days of occurrence, intensity, action taken, and whether the reaction led to early termination from the study, of solicited (prelisted in the subject's diary card and CRF) systemic reactions occurring up to D07 after each vaccination
- Occurrence, nature (MedDRA preferred term), time of onset, duration, intensity, action taken, relationship to vaccination, and whether the event led to early termination from the study, of unsolicited AEs up to D30 after each vaccination
- Occurrence, nature (MedDRA preferred term), time of onset, duration, seriousness criteria, relationship to vaccination, outcome, and whether the event led to early termination from the study, of SAEs (including AESIs) throughout the trial from D0 to the last study visit

Assessment Methods

At each vaccination visit, the Investigator or a delegate will perform a physical examination on the basis of relevant medical history according to the Investigator's clinical judgment and will ask the parent / guardian about any solicited reactions and unsolicited AEs recorded in the diary card, as well as about any other AEs that may have occurred since the previous visit. All relevant data will be transcribed into the CRB according to the instructions provided by the Sponsor.

4.3.2.3.1 Immediate Post-vaccination Observation Period

Subjects will be kept under observation for 30 minutes after each vaccination to ensure their safety. The post-vaccination observation should be documented in the source document. Any AE that occurs during this period will be noted on the source document and recorded in the CRB, as follows:

- Unsolicited systemic AEs will be recorded as immediate AEs in the CRB (presence marked as “yes” and details collected).
- Solicited and unsolicited injection site reactions and solicited systemic reactions will be recorded in the CRB in the same way as any reactions starting on the day of vaccination.
- SAEs will be recorded in the CRB and reported to the Sponsor in the same way as any other SAEs.

4.3.2.3.2 Reactogenicity (Solicited Reactions from Day 0 to Day 7 After Each Meningococcal Vaccination)

After the first vaccination, subject’s parents / guardians will be provided with a diary card, a digital thermometer, and a flexible ruler, and will be instructed how to use them. The following items will be recorded by the subjects in the diary card on the day of vaccination and for the next 7 days (i.e., D0 to D7) until resolution:

- Daily temperature, with the route by which it was taken
- Daily measurement or intensity grade of all other solicited injection site and systemic reactions
- Action taken for each event (e.g., medication)

The action(s) taken by the parent or guardian to treat and/or manage any **solicited reactions** will be classified in the CRB using the following list (all applicable items should be checked):

- None
- Medication
- Health care provider contact
- Hospitalized
- Discontinuation of study vaccination
- Whether the AE was related to the investigational product (for injection site events linked to routine pediatric vaccines)

The Investigator will assess the causal relationship between the AE and the investigational product as either “Not related” or “Related”.

Subject’s parents / guardians will be contacted by telephone 8 days after vaccination visit, to remind them to record all safety information in the diary card.

If the timing of the telephone call should fall on a weekend or a holiday, the call should be made on the next business day. If contact is not made on the designated day, study staff will continue calling until contact is made. Every telephone attempt and its outcome will be documented in the source document.

Table 4.1 and Table 4.2, respectively, present the injection site reactions and systemic reactions that are prelisted in the diary cards and CRB, together with the intensity scales.

Table 4.3: Solicited injection site reactions: terminology, definitions, and intensity scales

CRB term (MedDRA lowest level term [LLT])	Injection site tenderness	Injection site erythema	Injection site swelling
(MedDRA preferred term)	Injection site pain	Injection site erythema	Injection site swelling
Diary card term	Tenderness	Redness	Swelling
Definition	Pain when the injection site is touched or injected limb mobilized	Presence of a redness including the approximate point of needle entry	Swelling at or near the injection site Swelling or edema is caused by a fluid infiltration in tissue or cavity and, depending on the space available for the fluid to disperse, swelling may be either soft (typically) or firm (less typical) to touch and thus can be best described by looking at the size of the swelling
Intensity scale*	Grade 1: Minor reaction when injection site is touched Grade 2: Cries or protests when injection site is touched Grade 3: Cries when injected limb is mobilized, or the movement of the injected limb is reduced	Grade 1: > 0 to < 25 mm Grade 2: ≥ 25 to < 50 mm Grade 3: ≥ 50 mm	Grade 1: > 0 to < 25 mm Grade 2: ≥ 25 to < 50 mm Grade 3: ≥ 50 mm

* For the subjective reaction of tenderness, parents /guardians will record the intensity level (Grade 1, 2, or 3) in the diary card. For the measurable reactions of redness and swelling, they will record just the size of the reaction, and the classification as Grade 1, 2, or 3 will be assigned at the time of the statistical analysis.

Table 4.4: Solicited systemic reactions: terminology, definitions, and intensity scales

CRB term (MedDRA LLT)	Fever	Vomiting	Crying abnormal	Drowsiness	Appetite lost	Irritability
Data analysis term (MedDRA preferred term)	Pyrexia	Vomiting	Crying	Somnolence	Decreased appetite	Irritability
Diary card term	Temperature	Vomiting	Abnormal crying	Drowsiness	Loss of appetite	Irritability

Definition	Elevation of temperature to $\geq 38.0^{\circ}\text{C}^*$ ($\geq 100.4^{\circ}\text{F}$)	Vomiting does not include spitting up	Inconsolable crying without a determined reason	Reduced interest in surroundings, or increased sleeping	See intensity scale	An excessive response to stimuli: increased fussiness, whining, and fretfulness despite attempts to comfort the infant and despite caregiver responses that would normally be soothing
Intensity scale*	Grade 1: $\geq 38.0^{\circ}\text{C}$ to $< 38.5^{\circ}\text{C}$ or $\geq 100.4^{\circ}\text{F}$ to $< 101.3^{\circ}\text{F}$ Grade 2: $\geq 38.5^{\circ}\text{C}$ to $< 39.5^{\circ}\text{C}$ or $\geq 101.3^{\circ}\text{F}$ to $< 103.1^{\circ}\text{F}$ Grade 3: $\geq 39.5^{\circ}\text{C}$ or $\geq 103.1^{\circ}\text{F}$	Grade 1: 1 episode per 24 hours Grade 2: 2–5 episodes per 24 hours Grade 3: ≥ 6 episodes per 24 hours or requiring parenteral hydration	Grade 1: < 1 hour Grade 2: 1–3 hours Grade 3: > 3 hours	Grade 1: Sleepier than usual or less interested in surroundings Grade 2: Not interested in surroundings or did not wake up for a feed / meal Grade 3: Sleeping most of the time or difficult to wake up	Grade 1: Eating less than normal Grade 2: Missed 1 or 2 feeds / meals completely Grade 3: Refuses ≥ 3 feeds / meals or refuses most feeds / meals	Grade 1: Easily consolable Grade 2: Requiring increased attention Grade 3: Inconsolable

* For the Russian Federation, febrile illness is defined as temperature $\geq 37^{\circ}\text{C}$). A prospective subject should not be included in the study until the condition has resolved or the febrile event has subsided.

† For all reactions but fever, parents / guardians will record the intensity level (Grade 1, 2, or 3) in the diary card. For fever, they will record the body temperature, and the classification as Grade 1, 2, or 3 will be assigned at the time of the statistical analysis based on the unit used to measure the temperature and the intensity scale.

Important notes for the accurate assessment of temperature:

Parents / guardians are to measure body temperature once per day, preferably always at the same time. The optimal time for measurement is the evening, when body temperature is the highest. Temperature is also to be measured at the time of any apparent fever. The observed daily temperature and the route of measurement are to be recorded in the diary card and the highest temperature will be recorded by the site in the CRB. The preferred route for this study is axillary. Pre-vaccination temperature is also systematically collected by the investigator on the source document. Tympanic thermometers must not be used.

4.3.2.3.3 Unsolicited Adverse Events

In addition to recording solicited reactions, parents / guardians will be instructed to record any other medical events that may occur during the 30-day period following vaccination. Local reactions will be collected after all vaccinations. Space will be provided in the diary card for this purpose.

Information on SAEs will be collected and assessed throughout the study, from the time of vaccination to 30 days after the last vaccination or study visit. Any SAE occurring at any time during the study will be reported by the Investigator in the CRB according to the completion instructions provided by the Sponsor; this includes checking the “Serious” box on the AE CRF and completing the appropriate Safety Complementary Information CRFs. All information concerning the SAE is to be reported either as part of the initial reporting or during follow-up reporting if relevant information became available later (e.g., outcome, medical history, results of investigations, copy of hospitalization reports in case a subject experiences febrile convulsion (neurological event associating fever and seizure), the assessment will be performed according to the “Guideline for definition and collection of cases of febrile convulsion,” and this event will be considered an SAE.

For each unsolicited AE (whether serious or non-serious), the following information is to be recorded:

- Start and stop date^a

^a The stop date of all related AEs will be actively solicited. For other events, the investigator will provide the stop date when it becomes available. AEs for which no stop date was obtained during the course of the study will be considered as ongoing at the end of the study.

- Intensity of the event:
 - For measurable unsolicited AEs that are part of the list of solicited reactions, the size of the AE as well as the temperature for fever will be collected and analyzed based on the corresponding scale used for solicited reactions.
 - All other unsolicited AEs will be classified according to the following intensity scale:
 - Grade 1: A type of adverse event that is usually transient and may require only minimal treatment or therapeutic intervention. The event does not generally interfere with usual activities of daily living.
 - Grade 2: A type of adverse event that is usually alleviated with additional therapeutic intervention. The event interferes with usual activities of daily living, causing discomfort but poses no significant or permanent risk of harm to the research participant.
 - Grade 3: A type of adverse event that interrupts usual activities of daily living, or significantly affects clinical status, or may require intensive therapeutic intervention.
- Whether the AE was related to the investigational product (for unsolicited systemic AEs)

The Investigator will assess the causal relationship between the AE and the investigational product as either “Not related” or “Related”.
- Action taken for each AE (e.g., medication)

The action(s) taken by the parent or guardian to treat and/or manage any unsolicited AEs will be classified in the CRB using the following list (all applicable items should be checked):

 - None
 - Medication
 - Health care provider contact
 - Hospitalized
 - Discontinuation of study vaccination
- Whether the AE was serious

For each SAE, the investigator will complete all seriousness criteria that apply (outcome, elapsed time, and relationship to study procedures)

- Whether the AE caused study discontinuation

4.3.2.3.4 Adverse Events of Special Interest

An AESI is defined as event for which ongoing monitoring and rapid communication by the Investigator to the Sponsor must be done. The following AEs will be captured as AESIs throughout the study:

- Generalized seizures (febrile and non-febrile)
- Kawasaki disease
- Guillain-Barré syndrome
- Idiopathic thrombocytopenic purpura (ITP)

These events have been listed as AESIs based on the feedback received from the European Union regulators.

No safety concerns relating to these AESIs have been identified with the use of MenACYW conjugate vaccine in the completed clinical trials. Because of their medical importance and to ensure expedited communication to the Sponsor, these AESIs are to be considered and collected as SAEs and reported to the Sponsor according to the procedure described in Section 10 of the study protocol.

4.3.2.3.5 Assessment of Causality

The Investigator will assess the *causal relationship* between each unsolicited systemic AE and the product administered as either *not related* or *related*, based on the following definitions:

Not related – The AE is clearly / most probably caused by other etiologies such as an underlying condition, therapeutic intervention, or concomitant therapy; or the delay between vaccination and the onset of the AE is incompatible with a causal relationship; or the AE started before the first vaccination (screening phase, if applicable)

Related – There is a “reasonable possibility” that the AE was caused by the product administered, meaning that there is evidence or arguments to suggest a causal relationship

Note: By convention, all AEs reported at the injection site (whether solicited or unsolicited) and all solicited systemic AEs are considered to be related to the administered product and therefore are referred to as reactions and do not require the Investigator’s opinion on relatedness.

-
- Confidential/Proprietary Information
 - Page 46 of 67

Adverse events likely to be related to the product, whether serious or not, that persist at the end of the study will be followed up by the Investigator until their complete disappearance or the stabilization of the subject's condition. The Investigator will inform the Sponsor of the date of final disappearance of the event or the date of "chronicity" establishment.

4.4 Derived Endpoints: Calculation Methods

4.4.1 Safety

4.4.1.1 Solicited Reactions

4.4.1.1.1 Daily Intensity

All daily records for solicited reactions will be derived into daily intensity according to the following classification: None, Grade 1, Grade 2, Grade 3, or Missing (Unknown).

For the derivation of daily intensities, the following sequential steps will be applied:

- 1) Solicited reactions (except Fever/Pyrexia) with CRF presence recorded as "No" and with all daily records missing (Unknown) then all daily intensities will be derived as None.
- 2) For non-measurable solicited reactions, daily intensities will correspond to daily records reported in the clinical database. For measurable solicited reactions the daily measurements reported in the clinical database will be converted based upon the intensity scales defined in the protocol; this assumes a reaction that is too large to measure (non-measurable, "NM") is Grade 3. Note the intensity could be considered "None" (not a reaction) in the analysis despite being considered a reaction by the investigator

Note: The maximum intensity on the ongoing period is derived from the record of the maximum intensity/measurement after the end of the solicited period following the rule described above.

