4.4.1.1.3 Presence

Presence is derived from the maximum overall intensity over the time period considered:

- None: No presence
- Grade 1, Grade 2, or Grade 3: Presence
- Missing or Unknown: Missing presence

Participants with at least one non-missing presence for a specific endpoint will be included in the analysis. Conversely, those without a non-missing presence will not be included in the analysis of the endpoint.

The time period is displayed as D0-D3, D4-D7, D8 and later.

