4.4.1.5.5 Adverse Events Leading to Study Discontinuation

This information will be summarized as collected. A flag is available in the clinical database for all AEs in order to identify AEs leading to discontinuation before the end of active phase.

In general, the items that are counted are:

- Disposition table: A participant who, on the “Completion at End of Study” form question “What was the participant's status?” has “Adverse Event” checked.
- Safety overview table: A participant who has either on the “Completion at End of Study” form, question “What was the participant's status?” has “Adverse Event” checked or lists a solicited AE that has “Caused Study Termination” checked that is at least Grade 1 or an unsolicited AE that has “Caused Study Discontinuation” checked that is at least Grade 1 or missing and is within the time period indicated.
- System Organ Class (SOC)/Preferred Term (PT) table: A solicited AE that has “Caused Study Termination” checked that is at least Grade 1 or an unsolicited AE that has “Caused Study Discontinuation” checked that is at least Grade 1 or missing and is within the time period indicated.

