5.3 Handling of Missing Data and Outliers

5.3.1 Safety

No replacement will be done.

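### For solicited reactions other than fever, a CRF answer of No without daily records is kept as reaction-free, but a Yes without daily records is dropped; taken alone, this can only lower the any-grade rate

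*SAP*

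**What the plan says.** SAP 4.4.1.1.1 derives daily intensity in sequential steps. Step 1 covers "Solicited reactions (except Fever/Pyrexia) with CRF presence recorded as" No: such a reaction, "and with all daily records missing (Unknown) then all daily intensities will be derived as None". Step 2 relies on the daily records alone. For non-measurable reactions, "daily intensities will correspond to daily records reported in the clinical database". For measurable ones the daily measurements are converted with the intensity scales, and "this assumes a reaction that is too large to measure" is Grade 3. Neither step says what to do when the CRF answer is Yes and no daily record exists.

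SAP 4.4.1.1.2 takes the maximum of the daily intensities and does not say how Missing ranks against None. SAP 4.4.1.1.3 derives presence from that maximum and turns a Missing maximum into missing presence. "Conversely, those without a non-missing presence will not be included in the analysis of the endpoint".

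Three other places matter:

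- **Intensity scales (SAP Tables 4.3 and 4.4).** Redness and swelling start at "Grade 1: > 0 to < 25 mm". Tenderness and the systemic reactions other than fever also start at Grade 1, with no Grade 0.
- **Events leading to discontinuation (SAP 4.4.1.5.5).** An unsolicited AE counts if it is "checked that is at least Grade 1 or missing and is within the time period indicated". A solicited one needs at least Grade 1.
- **Missing safety data (SAP 5.3.1, and likewise Protocol 12.3.1).** "No replacement will be done".

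**The concern.** The same CRF field is used when it reports no reaction and not used when it reports one. For the non-fever reactions the scales give no ground for this. Any such reaction is at least Grade 1, so a Yes settles any-grade presence as fully as a No settles absence. Removing the Yes children makes exclusion depend on the outcome.

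The SAP treats unsolicited events the other way. Under 4.4.1.2.1 an event needs only a verbatim term and an intensity other than Grade 0. Under 4.4.1.2.4 a missing onset is placed within 30 days, and under 4.4.1.5.4 a missing relationship is taken as related.

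At stake are the any-grade rates of solicited reactions. These make up two of the five safety endpoints in SAP 4.3.2.2, and describing safety is the whole of the observational objectives.

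**Working it through.** The plan gives no figure for this rule, so there is none to reproduce. The check follows the rule and then sizes its effect.

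**Direction, reactions other than fever.** Let A be the reactors seen in daily records, N all children kept in the analysis (including each No without records, set to None), and y the children with Yes and no daily records.

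- Rate under the SAP: A/N.
- Rate if CRF presence were used for both answers: (A+y)/(N+y).

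Since A cannot exceed N, A/N ≤ (A+y)/(N+y). A grid of 203,390 combinations of counts gave no case in the other direction.

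**Size.** Let p be the true rate and a the fraction of reactors with Yes and no daily grade. The numerator falls from p to p(1-a) and the denominator from 1 to 1-pa:

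reported rate = p(1-a)/(1-pa)

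The documents give neither p nor a. Assumed values are p = 40% and 5%, and a = 2% to 10%.

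| a | p = 40% | p = 5% |
|---|---|---|
| 2% | 0.392/0.992 = 39.5% | 0.049/0.999 = 4.90% |
| 5% | 0.380/0.980 = 38.8% | 0.0475/0.9975 = 4.76% |
| 10% | 0.360/0.960 = 37.5% | 0.045/0.995 = 4.52% |

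In counts, for the planned 200 children of Group 1 and a = 10%: 80 reactors lose 8, so 80/200 = 40.0% becomes 72/192 = 37.5%; 10 reactors lose 1, so 10/200 = 5.0% becomes 9/199 = 4.5%. The relative loss, a(1-p)/(1-pa), is 0.06/0.96 = 6.3% and 0.095/0.995 = 9.5%. At a = 2% it is 0.012/0.992 = 1.2% and 0.019/0.999 = 1.9%.

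**Fever.** Step 1 does not apply, so a child with no temperatures is dropped whatever the CRF says. Take 60 children with fever and 130 without on daily records, plus 10 with none. The SAP rate is 60/190 = 31.6%. If the 10 are 8 No and 2 Yes, the rate by CRF presence is 62/200 = 31.0%, and the SAP is too high. If they are 4 No and 6 Yes, it is 66/200 = 33.0%, and the SAP is too low.

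**Neither a CRF answer nor daily records.** These children are dropped for every reaction. With 80 reactors, 110 non-reactors and 10 unknown, the SAP gives 80/190 = 42.1%, while the true rate lies between 80/200 = 40.0% and 90/200 = 45.0%. This too can go either way.

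**Partly completed card.** Suppose the reaction day is ungraded and the other days are None. If the maximum ignores Missing, the child counts as having no reaction. If Missing outranks None, the child is dropped. SAP 4.4.1.1.2 does not say which.

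**The case against.** The strongest defence is that the two answers carry different information. A No fixes every day at None; a Yes fixes no daily grade. That is true of the grade, and a reason not to invent one. It is not a reason to discard presence, which a Yes does establish for these scales.

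A second defence is that such records should be rare. Protocol 11.1 has staff interview parents and clarify incomplete entries, 11.2 applies consistency checks and queries, and 13.2 provides for verbal clarification of missing diary data. This stands as an argument about frequency. It does not remove the asymmetry, and late recall may produce the very case at issue: cards are collected at the next visit, scheduled 30 to 60 days after vaccination, when a parent may remember swelling but not its daily size.

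Third, the shift is small next to sampling error. At 40% with 200 children the 95% half-width is about 1.96 × √(0.4 × 0.6/200) = 6.8 points, against a shift of at most 2.5 points in the assumed range. That also stands, and the analysis is purely descriptive. But a systematic shift does not shrink with sample size, and the data to avoid it are already in the CRF.

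Four stronger readings are tempting, and the documents do not support them:

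- **All solicited reaction rates can only be biased downward.** Fever is excluded from step 1, and children with no CRF answer can move a rate either way.
- **An ungraded reaction on a partly completed card is certainly counted as no reaction.** That depends on an unstated ranking of Missing.
- **A child withdrawn for an ungraded solicited reaction vanishes from the discontinuation counts.** Under 4.4.1.5.5 an end-of-study status of Adverse Event still brings the child into the disposition and overview tables. Only the SOC/PT table can miss the reaction.
- **Step 1 contradicts 5.3.1.** Step 1 is a specific derivation from a recorded answer and 5.3.1 a general statement, so a cross-reference is enough.

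**Conclusion.** The concern holds for solicited reactions other than fever. Followed as written, SAP 4.4.1.1.1 and 4.4.1.1.3 keep a No without daily records and drop a Yes without daily records. The fate of the Yes is inferred from the absence of a rule together with step 2 and the presence rule, but the text leaves no other route.

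Taken alone, the asymmetry can only lower the any-grade rate. Its size rests on an assumed 2% to 10% of reactors without any daily grade: 40% is reported as 39.5% to 37.5%, and 5% as 4.90% to 4.52%. With diary clarification working, the effect is probably at the small end. The trial is open-label, so the share could in principle differ between arms, but nothing in the documents shows that it does. The point is worth correcting because the correction is cheap, not because the likely distortion is large.

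**What to change.** - **SAP 4.4.1.1.1 and 4.4.1.1.3.** For non-fever solicited reactions with CRF presence Yes and no daily record of Grade 1 or higher because daily records are missing, set presence to Yes and intensity to Missing. Count the child in the numerator and denominator of the any-grade rate, and add an intensity-missing row to the grade table.
- **SAP 4.4.1.1.2.** State how Missing enters the maximum, including when the remaining days are None.
- **SAP 4.4.1.5.5.** In the overview and SOC/PT rules, let a missing grade qualify for non-fever solicited reactions as it already does for unsolicited AEs.
- **SAP 5.3.1.** Refer to the derivations in 4.4.1.1 as the specific rules that apply.

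The cost is a few lines of SAP text and programming, with no new data. Any-grade rates may be slightly higher, and some reactions will appear without a grade. The change does not address fever, or children with neither a CRF answer nor daily records; reporting their number by group would show how much rests on them.
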